8. STUDY CALENDAR

Requi red Assess ment	Baseli ne visit		Treatme	nt visit #	6 th cycle F-U° Toler ability phase	8-10 week F-U	1 year F-U	2 year F-U					
								Rando ph					
		1	2	3	4	5	6	7	8				
Infor med Conse nt	V												
Inclus ion/e xclusi on criteri	V							\langle					
a Blood tests*	\checkmark	\checkmark		\checkmark			\checkmark						
Blood sampl e for genot yping		V											
Electr ocardi ogram (ECG) **	V	V	V	V	√	✓	V	V	V				
Rando mizati on	V			X									
Demo graph ic data collect ion	V												
RAND -12 and BPI questi onnai res	~							V		V	V		
Cognit ive testin g	V										V		
HADS questi onnai re	V												

NPSI questi onnai	V	V	V	V	\checkmark	V	V	V	V	V	V		
re Senso ry mappi	V	V	V	√	V	V	√	V	V	√	V		
ng QST** *	\checkmark			\checkmark				\checkmark		\checkmark	\checkmark		
Cold allody nia and dysest hesia	V	V	V	V	V	V	V	V	V	V	V		
PN gradi ng	V	V	V	V	\checkmark	V	V	V	\checkmark	V	V		
Study drug admin istrati on		V	V	V	V	V	V		V				
QLQ- CIPN2 0 assess ment		V	V	V	V	V	V	V	V	V	V		
Adver se effect monit oring ‡		V	V	V	V	Ň	V	V	V				
Serial blood sampl ing for PK*** *		V	V										
Single PK sampl e - at 130mi n				V	V	V	V	V	V				
Progr ession -free and overal l surviv al (medi cal												V	V
recor d													

ſ	revie							
	w)							

*Comprehensive metabolic panel (CMP). **ECG will be performed at baseline (12-lead) and monitored during study sessions (3-lead). *** For subjects participating at the satellite locations, the CPT test will not be performed. ‡ Adverse effects will be monitored during and 60 min after the study drug infusion. **** Serial blood sampling for PK collected during first 2 cycles of study drug, then a single PK sample at the remaining cycles. °A scheduled follow-up visit 2 weeks after the 6th treatment visit (immediately prior to the 7th) for patients in the tolerability phase. °° 8-10 weeks after the last cycle (or 12th, whichever earlier), an additional visit will be planned. BPI=Brief Pain Inventory. HADS = Hospital Anxiety and Depression Scale; NPSI = Neuropathic Pain Symptom Inventory; QST = Quantitative Sensory Testing; PK = Pharmacokinetics

9. **OBSERVATIONS AND MEASUREMENTS**

9.1. Primary Outcome Measures

Efficacy RCT: Oxaliplatin-induced Cold allodynia and dysesthesia as means of the intensity of unpleasantness (stinging and/or pricking) upon holding a pre-cooled (~8°C) metal cylinder (rod test) will serve as primary outcome measure, after the first 8 cycles of mFOLFOX6, and will be compared between Lidocaine and placebo groups.

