	7. Quality of life assessment using RAND-12										
	8. Cumulative oxaliplatin dose										
	9. Lidocaine plasma pharmacokinetics: blood sampling for lidocaine										
	concentration.										
	10. Genotyping for OIPN susceptibility										
Statistical	Efficacy pilot study: The intensity of stinging/pricking sensation										
Methodology	following a 10-second palm contact with a pre-cooled metal cylinder										
	(8°C) will serve as primary outcome measures. We expect that the IV										
	lidocaine intervention will result in a lower intensity of cold-induced										
	stinging/pricking compared to the placebo group. To detect a difference										
	between an intensity of $7(\pm 2.2)$ in the placebo group vs $4(\pm 2.2)$ in the										
	lidocaine group, on 0-10 numerical rating scale, thirteen patients per										
	group will allow detecting this difference with 90% power (two-sided t-										
	test, $a = 0.05$, effect size 1.36). We will enroll 30 subjects to account for										
	drop-outs.										

Table of Contents

S	YNOP	SIS	3
1.	BA	CKGROUND AND SIGNIFICANCE	7
	1.1.	Colorectal Cancer	7
	1.2.	Oxaliplatin	
	1.3.	Oxaliplatin-Induced Peripheral Neuropathy	
	1.4.	Lidocaine	
	1.5.	Preliminary Data	9
2.	OB	JECTIVES	9
3.	PA	TIENT SELECTION	10
	3.1.	Inclusion Criteria	10
	3.2.	Exclusion Criteria.	10
	3.3.	Inclusion of Women and Minorities	
4.	RE	GISTRATION PROCEDURES	11
	4.1.	Confirmation of Patient Eligibility	11
	4.2.	Patient Registration in the Siteman Cancer Center OnCore Database	11
	4.3.	Assignment of UPN	
	4.4.	Randomization	11
5.	STU	UDY DESIGN	11
6.	STU	UDY PROCEDURES	12
	6.1	Pre-Study Period	10
	6.1. 6.2.	Agent Administration	
	6.3.	Dose De-Escalation Schema for Tolerability Phase	
	6.4.	Definition of Maximum Tolerated Dose, Dose De-Escalation Criteria, and Toxicity and D	14 М Т
	0.4.	Evaluations	
	6.5.	Toxicity and DLT Evaluations	
	6.6.	Randomized Phase	
	6.7.	Blood for Determining Lidocaine Concentration	
	6.8.	Concomitant Medications and Supportive Care	
	6.9.	Women of Childbearing Potential.	
	6.10.	Duration of Therapy	
	6.11.	Duration of Follow-up	18
7.	DO	SE MODIFICATIONS	18
8.	STU	UDY CALENDAR	19
9.	OB	SERVATIONS AND MEASUREMENTS	21

9.1. 9.2.	Primary Outcome Measures
10. STA	ATISTICAL METHODS
10.1.	Sample Size
11. REG	GULATORY AND REPORTING REQUIREMENTS22
11.1. 11.2. 11.3.	Definitions
11.4.	Washington University 24 Timeframe for Reporting Required Events 24
12. DA	TA AND SAFETY MONITORING
13. REI	FERENCES

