5. STUDY DESIGN

The study has two phases: 1) a Tolerability phase and 2) a randomized, double-blind pilot phase to evaluate efficacy. In the tolerability phase, we plan to enroll 8 patients with Stage III or IV colorectal cancer treated with oxaliplatin in mFOLFOX6 regimen. In the randomized phase, 30 colorectal cancer patients will be randomized to infusion of intravenous Lidocaine HCl or identical placebo (in D5W-Dextrose 5% in water).

The patients in the mFOLFOX6 regimen receive their routine oxaliplatin treatment sessions every 2 weeks. In both phases, the assessments will be conducted at baseline, and at each of these 2-week visits, prior to oxaliplatin infusions (see summary in Table 2). Two additional visits are planned, the first will occur 2 weeks after the 6th treatment cycle (immediately prior to the 7th cycle) of

oxaliplatin, and the second will occur 8-10 weeks after the last (or 12th, whichever earlier) oxaliplatin treatment, and several assessment will be performed at both points (Table 2).

Lidocaine pharmacokinetics will be determined by serial blood sampling in both phases, for doseeffect relationship investigation. In the efficacy pilot phase, the full set of blood samples (multiple time-points) will be collected only during first 2 cycles of study drug intervention. A single sample at the end of lidocaine infusion (130 minutes) will be collected during the remaining intervention cycles to obtain the maximum plasma concentration (Cmax).

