6.6. Randomized Phase

In the randomized phase, 30 colorectal cancer patients will be randomized to infusion of intravenous lidocaine or identical placebo (D5W-Dextrose 5% in water), per regimen established in the dose-finding phase. The blinded infusions will be co-administered with oxaliplatin via Y-site [45] for all cycles of mFOLFOX6 protocol (approximately every 14 days). The patients are initially planned to receive the study drug for 8 of the 12 cycles of mFOLFOX6 treatment; if the treating clinician decides to reduce the number of treatment cycles to less than 8, the number of study interventions will be reduced accordingly.

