6.11. Duration of Follow-up

In the tolerability phase, patients will have a follow-up visit prior to their 7th cycle of mFOLOFX6, and an additional visit at 8-10 weeks after 12th (or last, whichever is earlier) dose of oxaliplatin. In the randomized phase, patients will have a follow-up visit at 8-10 weeks after 12th (or last, whichever is earlier) dose of oxaliplatin. The main purpose of these visits is to compare the development of persistent neuropathy and neuropathic pain between the two study arms. Patients removed from study for unacceptable adverse events will be followed until resolution or stabilization of the adverse event. One year and again at two years after enrollment in the study, progression-free and overall survival will be assessed by review of the medical record.

7. **DOSE MODIFICATIONS**

In case of mild (Grade 1 AE) tachy- or brady- arrhythmias, or oxygen desaturation, the infusion will be paused, and attempted to resume 10 minutes after resolution of the adverse effect. In any case of moderate (Grade 2+) to severe tachy- or brady- arrhythmias (except sinus tachycardia, which is defined as DLT if Grade 3+), or oxygen desaturation, the infusion will be stopped, and patient withdrawn from the study.

In any case of serious side effects, the study team will follow the American Society of Regional Anesthesia (ASRA) guidelines on systemic local anesthetic toxicity [43]. Intralipid[®] infusion for possible local anesthetic systemic adverse effect management will be readily available and carried by the study the team.

The following stopping rules will be applied:

Lidocaine is not known to affect liver or kidney function. However, if the subject develops renal insufficiency (Creatinine clearance <30 ml/min) or liver insufficiency (ALT or AST >3 times upper normal value in patients with no liver metastases, ALT or AST >5 times upper normal value in patients with liver metastases) for any reason, the study drug will not be administered at that oxaliplatin treatment session for safety reasons. If prior to subsequent cycles of chemotherapy the limiting kidney/liver function improves beyond the above criteria, the study drug can be administered with oxaliplatin, within the same mFOLFOX6 regimen.

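### Neuropathy itself can remove a patient's primary cold-cylinder rating, and the plan does not say which value counts for patients with fewer than 8 cycles

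*Combined protocol and SAP*

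**What the plan says.** **The primary outcome.** Section 9.1 states that the cylinder rating "will serve as primary outcome measure, after the first 8 cycles of mFOLFOX6, and will be compared between Lidocaine and placebo groups". Sections 10 and 10.1 repeat the 8-cycle timing for the randomised phase. Section 10.1 bases the power on the pricking/tingling intensity.

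**Where the rating comes from.** Section 10 gives patients rods to keep at home. They rate pain and pricking/tingling daily, on two separate 0-10 scales, through the 8 cycles and up to a two-week follow-up. Clinic assessments take place "at each of these 2-week visits, prior to oxaliplatin infusions" (section 5), so the test at visit 8 follows 7 doses. The next clinic visit listed for this phase is late: "In the randomized phase, patients will have a follow-up visit at 8-10 weeks after 12th (or last, whichever is earlier) dose of oxaliplatin" (section 6.11).

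**Fewer than 8 cycles.** Section 6.6 says: "The patients are initially planned to receive the study drug for 8 of the 12 cycles of mFOLFOX6 treatment". It allows for a shorter course ("if the treating clinician decides to reduce the number of treatment cycles to less than 8") and then cuts the number of study infusions to match. Section 6.2 ends mFOLFOX6 for persistent Grade 3 neuropathy. Section 6.8 withdraws patients from the study when their neuropathy needs drug treatment.

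**After stopping.** Section 6.10 follows patients who discontinue treatment early, whatever the reason, according to the study calendar. Their assessments on infusion days are left to the discretion of the investigator and the patient. The home diary is not mentioned there.

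**The concern.** The trial tests prevention of neuropathy, and two of its own rules let neuropathy end a patient's treatment or participation before the primary value is due. The patients most likely to lack a value would then be those who did worst. Sections 6.8 and 6.10 do not fit together clearly: one removes a patient from the study, the other follows patients who stop treatment, and neither says whether someone withdrawn under 6.8 keeps rating the cylinder. Nor does any section say what enters the comparison for a patient who never reaches cycle 8.

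If lidocaine works, placebo patients would be lost more often and their highest ratings would drop out of the placebo mean. The estimated difference would move towards zero, and a useful effect could be missed in a pilot meant to lead to a larger trial. A lesser issue is that the rating and summary within the two weeks after dose 8 are not fixed, so they could be chosen after data exist.

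**Working it through.** **1. The plan's own figure.** Inputs from section 10.1: means 7 and 4, SD 2.2 in each arm, two-sided t-test, alpha 0.05, power 90%.

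- Effect size = (7 − 4)/2.2 = 1.36, as stated.
- The exact (noncentral t) sample size is 12.35 per arm, rounded up to 13 per arm, or 26 in all. The plan's figure is reproduced.
- Power at 13 per arm is 91.5%.
- Enrolling 30 leaves room for 30 − 26 = 4 losses, or 4/30 = 13.3%.

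**2. Loss unrelated to the outcome.** With the same difference and SD, power is 95.0% at 15 per arm, 89.1% at 12 and 82.2% at 10. Loss of this kind costs precision but leaves the expected difference at 3.0.

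**3. What happens to the primary value, route by route.**

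| Route | Section | Study drug or follow-up | Primary rating |
|---|---|---|---|
| Clinician shortens chemotherapy below 8 cycles | 6.6 | Study infusions reduced to match | Not stated |
| Persistent Grade 3 neuropathy | 6.2 | mFOLFOX6 ends; 6.10 follow-up applies | Infusion-day tests discretionary; diary not mentioned |
| Neuropathy needing drug treatment | 6.8 | Withdrawn from the study; not clear whether 6.10 applies | Not stated |

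The second and third routes are triggered by the condition that the trial measures.

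**4. Size of outcome-related loss, as an assumption.** The documents give no early-stop rate, so this is illustration only. Take 15 per arm, normal ratings with means 7 and 4 and SD 2.2, a t-test on the available values, and 60,000 simulated trials. Remove k of the 15 placebo ratings and none on lidocaine.

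| k lost on placebo | Difference, highest k lost | Power, highest k lost | Power, k lost at random |
|---|---|---|---|
| 0 | 3.0 | 95.0% | 95.0% |
| 1 | 2.73 | 91.4% | 94.4% |
| 2 | 2.50 | 86.2% | 93.4% |
| 3 | 2.28 | 79.1% | 92.2% |

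Check on the last row: a difference of 2.28 means that the remaining 12 placebo ratings average 4 + 2.28 = 6.28. The 3 removed must then average (15 × 7 − 12 × 6.28)/3 = (105 − 75.36)/3 = 9.88, near the top of the scale. Three losses are within the plan's own allowance of 4, so the allowance protects power only if losses are unrelated to the rating.

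**5. How much choice is left within the window.** At 14-day cycles about 14 daily ratings follow dose 8, and the plan does not say whether one of them, a mean or a peak is used. If a mean is chosen, the SD of 2.2 need not carry over. With an assumed day-to-day correlation of 0.5 to 0.9, a 14-day mean has SD = 2.2 × √((1 + 13ρ)/14), which is 1.61 to 2.10.

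**The case against.** The strongest reply is that the plan is less open than it looks, and much of that reply stands.

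- **A reader might infer that nothing governs patients with fewer than 8 cycles.** That goes too far. Section 6.6 covers their study infusions and section 6.10 their follow-up. What is missing is narrower: the value used in the primary comparison, and whether the diary continues.
- **A reader might infer that nothing is measured after cycle 8.** The diary covers that period. The natural reading of the two-week follow-up in section 10 is two weeks after the last study cycle in each phase. The only visit described in those terms follows cycle 6 and belongs to the tolerability phase, which is a reason to clarify the phrase and not evidence of a gap in the data. With the diary as source, the absence of a listed clinic test just after dose 8 matters little. Section 5 could also be read to include a test before cycle 9.
- **A reader might infer that several different primary outcomes are named.** The stinging, pricking, tingling and unpleasantness terms are best read as loose wording for the pricking/tingling rating that section 10.1 powers.
- **The bias is not demonstrated.** Stopping depends on persistent Grade 3 neuropathy or need for medication, not on a cylinder score, so deleting exactly the highest ratings is close to a worst case for that number of losses. Section 7 also withdraws patients for arrhythmia or oxygen desaturation, a route not tied to the rating. This limits what can be said about size. It does not close the route by which neuropathy removes the value.

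The trial calls itself a pilot, which limits how serious the point is. It still has one powered comparison in about 30 patients, where a few selective losses matter.

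**Conclusion.** The point holds in this form: followed as written, sections 6.2, 6.8 and 6.10 allow the primary rating to be missing because of neuropathy, and no section says which value represents a patient with fewer than 8 cycles. It should be fixed before unblinding.

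The direction, a diluted difference, rests on two assumptions: that lidocaine works, and that patients who stop for neuropathy give no later rating and tend to have high scores. The size cannot be derived from the documents. The fall to a difference of about 2.3 and power of 79% is an illustration of 3 selective placebo losses, not a forecast. The sample size calculation is correct and needs no change. The undefined rating and summary within the window is a secondary matter of missing detail, to be settled in the same edit.

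**What to change.** Before unblinding:

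1. **Keep collecting the rating.** Reconcile 6.8 with 6.10 so that home-diary ratings continue through the primary window for every randomised patient who stops treatment or is withdrawn for neuropathy. This is a data-collection change and alters no treatment rule. Include all randomised patients with their observed ratings, and flag those made after neuropathy medication starts.
2. **Fix the primary value.** In the Synopsis and in sections 9.1, 10 and 10.1, name the home 0-10 pricking/tingling rating as the single primary variable. Give it one window, in the two weeks after the 8th oxaliplatin dose or after the last dose if fewer than 8 are given, and one summary. State that this window ends at the two-week follow-up of section 10. Anchor it to oxaliplatin and not to study drug, because section 7 provides that in renal or liver insufficiency "the study drug will not be administered at that oxaliplatin treatment session for safety reasons". If a mean is chosen, say that 7 versus 4 with SD 2.2 may not carry over.
3. **Add a suitable sensitivity analysis.** Give unfavourable values to patients whose rating is missing after a neuropathy-related stop, for example by a rank test with worst ranks. An analysis limited to patients who received 8 doses would not serve: it selects on a post-randomisation event that neuropathy can cause, and so repeats the bias under test.

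A clinic cylinder test two weeks after dose 8 is optional.

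**Cost.** The work is mainly protocol and analysis-plan wording, since the diary is already planned. Patients who stop early must keep a short diary, and the last-dose anchor mixes different oxaliplatin exposures among those with fewer than 8 cycles.

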9.2. Secondary Outcome Measures

1. Occurrence of Grade 2+ peripheral neuropathy during treatment, measured by NCI-CTC Peripheral Neuropathy Grading;

- 2. Time to event (Grade 2+ peripheral neuropathy)
- 3. Change in CIPN score (on EORTC QLQ-CIPN20 tool) over time until last follow-up;
- 4. Magnitude of sensory disturbances on QST (change from baseline to last follow-up);

5. Changes in NPSI descriptors of neuropathic pain over time from baseline to last follow-up (NPSI will be administered separately for pain in feet and for pain in hands).

7. Change in Mental and Physical summary scores on RAND-12 questionnaire [37] from baseline to last follow-up;

- 8. Pain intensity on 0-10 numerical rating scale at each treatment day, and last follow-up.
- 9. The cumulative dose of oxaliplatin over the course (up to 12 cycles) of mFOLFOX6

10. Two-year progression-free and overall survival determined by medical record review.

9.3. Exploratory outcome Measures

Determination of a possible association between the development of OIPN and the existence of gain-/ or loss-of-function single nucleotide polymorphisms (SNPs) for the following targets will be conducted in collaboration with the Washington University Genome Technology Access Center: 1. Voltage-gated sodium channels: Nav 1.4 (SCN4A gene), Nav 1.6 (SCN8A gene), (Nav 1.7 (SCN9A gene)), and Nav 1.8 (SCN10A gene), that are associated with painful neuropathies. 2. Glutathione-s-transferase: GST π -gene (GSTP1), GST μ 1-gene (GSTM1), and GST θ 1-gene (GSTT1), that may affect the development of severe oxaliplatin related neuropathy.

10. STATISTICAL METHODS

Ideally, the primary outcome of the clinical trial would be the comparison of disability caused by painful OIPN between the study arms, or progression-free survival of the patients for the prevention

of dose-limiting OPIN with lidocaine. However, to have sufficient power to detect these clinicallyrelevant outcomes of pain and chemotherapy effectiveness, we would require approximately 60 and 78 patients per group, respectively. This would be the goal of the future extramurally-funded clinical trial. In this pilot trial, we have defined our primary outcome as the intensity of unpleasantness of cold-induced stinging/pricking after 6 cycles in the tolerability phase and 8 cycles in the randomized phase of mFOLFOX6 and the study intervention.

Oxaliplatin-induced peripheral neuropathy is associated with characteristic patterns of distal tingling sensations and cold-evoked pain (cold-allodynia), the severity of which is an indicator of long-term neuropathy and neuropathic pain [24]. Conventional nerve conduction studies lack the power to accurately detect early symptoms of cold allodynia. Recently, a cold hypersensitivity method has been developed to determine the severity of oxaliplatin-induced peripheral neuropathy, using the application of standardized pre-refrigerated metal rods on the palmar surface [24] and measuring the severity of cold allodynia after 10 seconds of contact.

Patients will be provided with such rods to place in their home refrigerator, and the results of daily assessment of cold allodynia will be recorded during 6 cycles in the tolerability phase and 8 cycles in the randomized phase of mFOLFOX6 treatment and up to the 2-week follow-up. We will provide patients with scoring sheets and ask to rate the intensity of pricking/tingling and pain after holding the pre-cooled cylinder each day at a standardized time. The intensity will be reported on two separate 0 - 10 numeric rating scales; one for pain (0 = no pain, 10 = worst pain imaginable), and one for pricking/tingling (0 = no pricking/tingling, 10 = worst pricking/tingling imaginable).

10.1. Sample Size

To demonstrate a significant difference between Lidocaine and Placebo on oxaliplatin induced cold-allodynia after the first 8 cycles (intensity of pricking/tingling after 10 second contact will 8°C cylinder 7(\pm 2.2) in the placebo group vs. 4(\pm 2.2) in the lidocaine group [24]), with a two-sided t-test, assuming α =0.05 and 90% power (effect size 1.36), 26 evaluable subjects (13 per arm) will be required to participate in the study. We will enroll 30 evaluable subjects to the study due to potential drop-outs.

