6.2. Agent Administration

At each of the intervention visits, an intravenous line used for oxaliplatin administration will be used for lidocaine administration, and a new IV line will be inserted in an arm for obtaining blood samples to evaluate the plasma concentrations of lidocaine. Lidocaine can be infused via Y-site through the same central/peripheral catheter as oxaliplatin, so that only one additional line will be placed for blood collection for the first 2 cycles of study drug administration. During the remaining

study visits, only a single blood sample will be obtained for lidocaine plasma concentration analysis. This will be done by venipuncture, without the requirement of an additional IV line.

The participants will receive the following mFOLFOX6 treatment regimen:

Oxaliplatin 85mg/m² IV over 2h on day 1,

Leucovorin 400 mg/m² IV over 2h on day 1,

5-FU 400mg/m² IV bolus on day 1, followed by a 1200mg/m²/day continuous infusion for 46 hours. This cycle is repeated every two weeks for six cycles in the tolerability phase and 8 cycles in the randomized phase with reevaluation for the maintenance therapy.

mFOLFOX6 will be the primary treatment regimen, however, variations of mFOLFOX6 regimen per treating physician (e.g., lack of administration of Leucovorin or 5-FU bolus in metastatic patients, or the addition of bevacizumab or irinotecan), will be acceptable.

In case of development of DLTs after oxaliplatin, dose de-escalation will occur.

mFOLFOX6 dose modification in the case of peripheral neuropathy:

The initial dose of oxaliplatin is 85mg/m^2 every 2 weeks. If a persistent (> 2weeks) Grade II Peripheral Neuropathy (PN) develops, the dose of oxaliplatin in mFOLFOX6 protocol will be reduced to 65mg/m^2 . If a persistent Grade 3 PN is present, mFOLFOX6 treatment will be discontinued.

mFOLFOX6 dose changes for reasons other than peripheral neuropathy are subject to treating clinician's decision; however, every dose change will be documented in the CRF.

Intravenous (IV) lidocaine will be dosed as a brief 1 mg/kg infusion (based on Ideal Body Weight (IBW)) over 10 minutes, followed by a 0.04 mg/kg/min infusion over additional 120 minutes. Lidocaine administration will begin 10 minutes prior to oxaliplatin initiation. The study drug administration will begin with the first cycle of oxaliplatin therapy.

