6.8. Concomitant Medications and Supportive Care

The patients will continue their chronic medications; including chronic pain medications, provided the dose have been stable for at least 2 weeks. If any of these medications are discontinued during the study, the changes will be recorded. PRN analgesics will not be limited, but their consumption will be carefully recorded. Addition of new medications for treating painful neuropathy (i.e. gabapentin, pregabalin, duloxetine, venlafaxine, tricyclic antidepressants, opioids) will not be allowed during the study. Patients will be withdrawn from the study if the peripheral neuropathy is severe enough to require pharmacological treatment.

Participation in the study will not be allowed if participants are treated with any of the following medications, which may result in serious drug-drug interaction with lidocaine:

- Saquinavir, Lopinavir, Amprenavir, Atazanavir, Delavirdine
- Mexiletine
- Phenytoin, Carbamazepine, Oxcarbazepine, Lamotrigine

- Amiodarone
- Dronedarone
- Dihydroergotamine
- Cimetidine

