6.10. Duration of Therapy

If at any time the constraints of this protocol are considered to be detrimental to the patient's health and/or the patient no longer wishes to continue protocol therapy, the protocol therapy should be discontinued and the reason(s) for discontinuation documented in the case report forms.

In the absence of treatment delays due to adverse events, treatment will continue for up to 6 cycles in the tolerability phase and 8 cycles in the randomized phase of mFOLFOX6 or until one of the following criteria applies:

- Documented and confirmed disease progression
- Death
- Adverse event(s) that, in the judgment of the investigator, may cause severe or permanent harm or which rule out continuation of study drug
- General or specific changes in the patient's condition render the patient unable to receive further treatment in the judgment of the investigator
- Suspected pregnancy
- Serious non-compliance with the study protocol
- Lost to follow-up
- Patient withdraws consent
- Investigator removes the patient from study
- The Siteman Cancer Center decides to close the study

Patients who prematurely discontinue treatment for any reason will be followed as indicated in the study calendar. On infusion days, those patients who are not receiving study drug will still undergo pre and post-infusion assessments per PI and patient discretion. All subjects will be followed up to two years for the collection of survival data.

During the tolerability phase the study will continue for 6 cycles of mFOLFOX6. If the patient and the treating physician wish to continue lidocaine co-infusions with additional cycles of oxaliplatin, intravenous lidocaine can be prescribed at the discretion of the treating physician.

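### No primary analysis or missing-score rule is stated; if the sample-size t-test were used on one post-cycle-8 cold score, neuropathy-related losses would dilute a true lidocaine effect

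*Combined protocol and SAP*

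**What the plan says.** **Analysis.** Section 9.1 says the cold score will be taken "after the first 8 cycles of mFOLFOX6, and will be compared between Lidocaine and placebo groups" and names no method. Section 10 describes the cooled rods and the 0-10 scales, but gives no model, analysis population, covariate or missing-score rule. The two-sided t-test appears only in the power statements (synopsis and section 10.1: "in the lidocaine group [24]), with a two-sided t-test, assuming").

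**Numbers.** Section 10.1 needs 26 evaluable patients, 13 per arm. It then describes 30 both as evaluable and as cover for drop-outs. It does not define evaluable.

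**Scores collected.** Section 5 states that "the assessments will be conducted at baseline, and at each of these 2-week visits, prior to oxaliplatin infusions". The calendar in section 8 lists the cold test at baseline, visits 1-8 and follow-up. Section 10 adds daily home ratings over the 8 randomised-phase cycles.

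**Ways to lose the score.** Section 6.8: "Patients will be withdrawn from the study if the peripheral neuropathy is severe enough to require pharmacological treatment". Section 6.6 lets the treating clinician give fewer than 8 cycles. Section 6.2: "If a persistent Grade 3 PN is present, mFOLFOX6 treatment will be discontinued". Against this, section 6.10 says "Patients who prematurely discontinue treatment for any reason will be followed as indicated in the study calendar", and on infusion days "those patients who are not receiving study drug will still undergo pre and post-infusion assessments per PI and patient discretion".

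**Timing.** In the randomised phase, section 6.11 places the follow-up visit 8-10 weeks after the last or 12th oxaliplatin dose, whichever comes first. The only 2-week visit in the calendar is a "scheduled follow-up visit 2 weeks after the 6th treatment visit (immediately prior to the 7th) for patients in the tolerability phase".

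**The concern.** With no analysis stated, a reader falls back on the one test that is named. On a single end-of-treatment score, a t-test includes only patients who have that score.

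Section 6.8 removes patients because of the condition that the primary outcome measures. If lidocaine prevents neuropathy, more placebo than lidocaine patients would leave this way, and they would tend to be the high scorers. The placebo patients who remain then look milder than the placebo arm as randomised, and the difference shrinks. Enrolling 30 for 26 covers the number lost (up to 4) but not this selection. For patients given fewer than 8 cycles, a score after the first 8 cycles is not defined at all.

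The record is open as well. The visit-8 score, one home day, a home average and the late follow-up visit could each be called the post-cycle-8 score. In a 30-patient trial, that choice should not be made after the data are seen.

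**Working it through.** **1. The plan's own figure.** Inputs (section 10.1): means 7 and 4, SD 2.2, two-sided alpha 0.05, power 90%.

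- Effect size d = (7 - 4)/2.2 = 1.364.
- Two-sample t-test, noncentral t: n = 12.35, rounded up to 13 per arm, 26 in total. This reproduces the plan.
- Power with n scores per arm: noncentrality d x sqrt(n/2), df 2n - 2. At n = 13, noncentrality is 3.477, df 24, power 91.5%. At n = 15, power is 95.0%; at 11, 86.0%; at 10, 82.2%.

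**2. Which record is the post-cycle-8 score?**

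- Clinic scores precede infusions, so the visit-8 score follows 7 doses.
- The next randomised-phase calendar visit is 8-10 weeks after dose 8 if treatment ends there. If 12 cycles are given, it is (12 - 8) x 2 + 8 to 10 = 16-18 weeks after dose 8.
- Cycles last 14 days, so daily home ratings during cycle 8 do cover the 2 weeks after dose 8. No day or summary of them is chosen, and no home rating before dose 1 is stated.

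**3. What outcome-related loss would do.** The documents give no loss rate, trigger or correlations, so everything here beyond the means and SD is an assumption. Simulation: 15 per arm; mean rising linearly from 2 at baseline to 7 (placebo) or 4 (lidocaine); SD 2.2; normal scores not bounded at 0-10; three correlation structures (autoregressive 0.85; 0.5 plus autoregressive 0.6; exchangeable 0.5); 1,000 trials per setting. The comparison model uses scores at cycles 2, 4, 6 and 8 with baseline, unstructured covariance, REML and Kenward-Roger degrees of freedom. Ranges run over the three structures.

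| Loss setting | t-test: difference / power | Model: difference / power |
|---|---|---|
| None | 2.97-2.98 / 92.8-94.0% (exact 95.0%) | 2.98-2.99 / 93.9-98.3% |
| (a) After a recorded score of 9 or more | 2.58-2.63 / 86.5-87.6% | 2.87-2.93 / 93.1-97.1% |
| (b) Trigger correlated 0.5 with the rod score | 2.75-2.81 / 87.5-88.9% | 2.90-2.96 / 93.3-96.7% |
| (c) Half of the patients in (a) leave | 2.79-2.81 / 90.6-90.7% | 2.93 / 92.9-97.1% |
| (d) Leave before the high score is recorded | 2.24-2.30 / 76.9-83.0% | 2.57-2.60 / 89.2-93.3% |

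Mean patients lost: in (a), 2.1-2.7 placebo and 0.3-0.4 lidocaine; in (d), 3.3-4.2 placebo. Repeating the t-test for (a), (c) and (d) with 4,000 trials gave power of 88-89%, 92-93% and 78-83%, so the t-test column may be about 1-2 points low. Part of the model's gain is ordinary baseline adjustment, which helps even with no loss.

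**4. False positives.** With no true difference, the t-test rejects in 4.3-6.3% of trials and the four-cycle model in 4.4-5.9% (Monte Carlo error about 0.7 points). Loss then falls equally on both arms.

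**5. Cost of adjusting for baseline.** With 13 per arm, df 23 and noncentrality 3.477 / sqrt((1 - r^2) x 23/22), power is 90.2% at baseline correlation r = 0, 92.7% at r = 0.3 and 96.4% at r = 0.5.

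**The case against.** **The documents never make the t-test the analysis.** This stands. A reader might infer that the trial will be analysed by a t-test in patients with a final score. The test appears only in power statements, and it could equally be run on each patient's mean of the daily ratings. The harm is therefore conditional.

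**The harm is modest and the loss settings are invented.** This largely stands. In (a)-(c) the t-test keeps about 87-91% power against a planned 90%. Only (d) falls clearly below, and there the model is diluted too. The actual trigger in section 6.8 is need for drug treatment, not a rod score of 9. The direction of the bias follows from the rule; its size does not.

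**A record does exist for the 2 weeks after dose 8.** This stands. A reader might infer that nothing covers that period, but the cycle-8 home ratings do. A clinic score before cycle 9 is a possible reading of section 5, although the calendar stops at visit 8. What is missing is the choice.

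**Sections 6.8 and 6.10 need not conflict.** This stands. One concerns withdrawal from the study, the other stopping treatment. Nor does stopping chemotherapy for persistent Grade 3 neuropathy by itself remove the score, because section 6.10 keeps such patients in calendar follow-up. Still unstated is whether scores are taken after a section 6.8 withdrawal; infusion-day assessments after stopping are discretionary.

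**A repeated-measures model is heavy for 30 patients.** This stands in part. At four cycles it has 12 mean and 10 covariance parameters, 22 in all. It is one option. Using the scheduled scores matters more than this exact model.

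**It is a pilot.** This does not answer the point. Section 10.1 sizes a two-sided 5% comparison, and section 10 looks ahead to a larger trial that a diluted estimate would inform poorly.

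**Conclusion.** The point holds in conditional form and should be fixed. The primary analysis, its population, the score record and the missing-score rule are all unstated. If the sample-size t-test were used on one post-cycle-8 score, the section 6.8 rule would tend to dilute a real effect. Under the assumed settings a true difference of 3 is estimated at about 2.2-2.8, with power about 77-91% instead of 95% at 15 per arm.

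The direction rests on lidocaine working and on withdrawn patients having no score. The size rests wholly on assumed loss and correlations, so it is illustrative, and with few withdrawals it would be small. Whether non-evaluable patients are replaced is also unclear, because 30 is described in two ways; replacement would restore numbers but not undo the selection.

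Two stronger readings are not supported. The sample size is not wrong: 13 per arm reproduces with 91.5% power. False positives are not inflated by this loss: the rate stays near 5%.

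**What to change.** Add a short paragraph to section 10 before unblinding, with planned n unchanged:

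1. **Score.** Define the primary score, for example the mean home pricking/tingling rating over the 2 weeks after dose 8, and say what is used for patients given fewer than 8 cycles. Say whether 30 is the number enrolled or the number evaluable.
2. **Primary analysis.** Name one that includes all randomised patients with a baseline and at least one later score and uses the earlier scores. An example is a repeated-measures model at a few pre-set cycles (such as 2, 4, 6 and 8) with cycle, arm-by-cycle and baseline-by-cycle terms, unstructured covariance and Kenward-Roger degrees of freedom, reporting the arm contrast after cycle 8. If another model is preferred, check its error rate first: a version with one constant variance and one baseline slope over all 8 cycles rejected a true null in 3.1-9.7% of simulated trials, and in 11.0-15.6% when the SD rose from 1.1 to 2.2.
3. **Sensitivity.** Keep the observed-score t-test, and add one analysis that shifts the scores of patients who left early.
4. **Collection.** State whether cold scores are still collected, and included, after a section 6.8 withdrawal or after treatment stops.

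**Cost.** If baseline is unrelated to outcome, power at 13 per arm falls from 91.5% to about 90%. That is possible, because section 3.2 excludes painful neuropathy and recent chemotherapy, so baseline scores may be low. The model reduces the dilution but does not remove it. A home baseline would need ratings before dose 1; otherwise the clinic baseline serves and no new data are needed.
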